4.5.9.3 Optional Patient Interviews

Patient interviews will be conducted among a subset of study participants (up to 30 patients in GDC-9545 arm) following Cycle 2 (this can potentially include the post-treatment period). The semi-structured interviews will be moderated by an external vendor and conducted by telephone (lasting up to an hour in duration). The interviews will explore participants’ experience of study treatment, therapeutic context, and disease journey. Recording from the interviews will be transcribed and de-identified to maintain confidentiality. Additional consent for this optional study component will be included in the relevant Informed Consent Form.

4.5.10 Blood Samples for Whole Genome Sequencing or Whole Exome Sequencing (Patients at Participating Sites)

At participating sites, blood samples will be collected for DNA extraction to enable WGS or WES to identify variants that are predictive of response to study drug, are associated with progression to a more severe disease state, are associated with acquired resistance to study drug, are associated with susceptibility to developing adverse events, can lead to improved adverse event monitoring or investigation, or can increase the knowledge and understanding of

disease biology and drug safety. Research will be aimed at exploring inherited characteristics. WES and WGS are not applicable in China.

DNA extracted from blood and plasma may be compared with DNA extracted from tissue to identify somatic variants by distinguishing germline variants from somatic variants. The samples may be sent to one or more laboratories for analysis.

Collection and submission of blood samples for WGS or WES is contingent upon the review and approval of the exploratory research by each site's Institutional Review Board or Ethics Committee (IRB/EC) and, if applicable, an appropriate regulatory body. If a site has not been granted approval for WGS or WES, this section of the protocol (Section [4.5.10](#)) will not be applicable at that site.

Genomics is increasingly informing researcher's understanding of disease pathobiology. WGS and WES provide a comprehensive characterization of the genome and exome, respectively, and, along with clinical data collected in this study, may increase the opportunity for developing new therapeutic approaches or new methods for monitoring efficacy and safety or predicting which patients are more likely to respond to a drug or develop adverse events. Data will be analyzed in the context of this study but may also be explored in aggregate with data from other studies. The availability of a larger dataset will assist in identification and characterization of important biomarkers and pathways to support future drug development.

For sampling procedures, storage conditions, and shipment instructions, see the laboratory manual.

Blood samples collected for WGS or WES are to be stored until they are no longer needed or until they are exhausted. However, the storage period will be in accordance with the IRB/EC-approved Informed Consent Form and applicable laws (e.g., health authority requirements).

Refer to Section [4.5.7](#) for details on use of samples after patient withdrawal, confidentiality standards for data, and availability of data from biomarker analyses.

4.5.11 Optional Tumor Biopsy (Patients at Participating Sites)

At participating sites, consenting patients will undergo an optional tumor biopsy at time of disease progression (see [Appendix 3](#)). Tumor biopsies of the growing lesion are preferred. Patients may undergo additional on-treatment biopsies at any other time at the investigator's discretion (if deemed clinically feasible by the investigator). Samples collected via resection, core-needle biopsy (at least three cores preferred), or excisional, incisional, punch, or forceps biopsy are preferred. Optional tumor biopsy at time of disease progression is not applicable in China.

The Informed Consent Form will contain a separate section that addresses optional biopsies. A separate, specific signature will be required to document a patient's agreement to undergo optional biopsies. The investigator should document whether or not the patient has given consent to participate and (if applicable) the date(s) of consent, by completing the Optional Biopsy Sample Informed Consent eCRF.

Samples may be used for exploratory biomarker research as described in Section [4.5.7](#). For sampling procedures, storage conditions, and shipment instructions, see the laboratory manual. Refer to Section [4.5.7](#) for details on duration of sample storage, use of samples after patient withdrawal, confidentiality standards for data, and availability of data from biomarker analyses.

Tumor specimen may be used for centralized retrospective assessment to evaluate correlation between genes, proteins, DNA, and RNA relevant to the signaling pathways and sensitivity/resistance to the investigational agents.

NGS may be performed by Foundation Medicine or an alternative, approved central laboratory for that region on tumor biopsies collected at time of disease progression. If performed by Foundation Medicine, the investigator may obtain an NGS report through Foundation Medicine's web portal for results from testing performed on tissue submitted at the time of disease progression. If allowed by local laws, the investigator may share and discuss the results with the patient, unless the patient chooses otherwise. The NGS report is generated for research purposes and is not provided for the purpose of guiding future treatment decisions. Results will not be available for samples that do not meet criteria for testing.

4.5.12 Optional Samples for Research Biosample Repository

4.5.12.1 Overview of the Research Biosample Repository

The Research Biosample Repository (RBR) is a centrally administered group of facilities used for the long-term storage of human biological specimens, including body fluids, solid tissues, and derivatives thereof (e.g., DNA, RNA, proteins, peptides). The collection, storage, and analysis of RBR samples will facilitate the

rational design of new pharmaceutical agents and the development of diagnostic tests, which may allow for individualized drug therapy for patients in the future. RBR is not applicable in China.

Samples for the RBR will be collected from patients who give specific consent to participate in this optional research. RBR samples will be analyzed to achieve one or more of the following objectives:

- To study the association of biomarkers with efficacy or disease progression
- To identify safety biomarkers that are associated with susceptibility to developing adverse events or can lead to improved adverse event monitoring or investigation
- To increase knowledge and understanding of disease biology and drug safety
- To study drug response, including drug effects and the processes of drug absorption and disposition
- To develop biomarker or diagnostic assays and establish the performance characteristics of these assays

4.5.12.2 Approval by the Institutional Review Board or Ethics Committee

Collection, storage, and analysis of RBR samples is contingent upon the review and approval of the exploratory research and the RBR portion of the Informed Consent Form by each site's IRB/EC and, if applicable, an appropriate regulatory body. If a site has not been granted approval for RBR sampling, this section of the protocol (Section [4.5.12](#)) will not be applicable at that site.

4.5.12.3 Sample Collection

The following samples will be stored in the RBR and used for research purposes, including, but not limited to, research on biomarkers related to GDC-9545, diseases, or drug safety:

- Leftover blood, plasma, and tumor tissue samples (with the exception of remaining archival tissue blocks, which will be returned to sites) and any derivatives thereof (e.g., DNA, RNA, proteins, peptides)

The above samples may be sent to one or more laboratories for analysis of germline or somatic variants via WGS, WES, or other genomic analysis methods. Genomics is increasingly informing researcher's understanding of disease pathobiology. WGS and WES provide a comprehensive characterization of the genome and exome, respectively, and, along with clinical data collected in this study, may increase the opportunity for developing new therapeutic approaches or new methods for monitoring efficacy and safety or predicting which patients are more likely to respond to a drug or develop adverse events.

Data generated from RBR samples will be analyzed in the context of this study but may also be explored in aggregate with data from other studies. The availability of a larger dataset will assist in identification and characterization of important biomarkers and pathways to support future drug development.

For sampling procedures, storage conditions, and shipment instructions, see the laboratory manual.

RBR samples are to be stored until they are no longer needed or until they are exhausted. However, the RBR storage period will be in accordance with the IRB/EC-approved Informed Consent Form and applicable laws (e.g., health authority requirements).

4.5.12.4 Confidentiality

RBR samples and associated data will be labeled with a unique patient identification number.

Patient medical information associated with RBR samples is confidential and may be disclosed to third parties only as permitted by the Informed Consent Form (or separate authorization for use and disclosure of personal health information) signed by the patient, unless permitted or required by law.

Given the complexity and exploratory nature of the analyses of RBR samples, data derived from these analyses will generally not be provided to study investigators or patients unless required by law. The aggregate results of any conducted research will be available in accordance with the effective Sponsor policy on study data publication.

Data generated from RBR samples must be available for inspection upon request by representatives of national and local health authorities, and Sponsor monitors, representatives, and collaborators, as appropriate.

Any inventions and resulting patents, improvements, and/or know-how originating from the use of the RBR data will become and remain the exclusive and unburdened property of the Sponsor, except where agreed otherwise.

4.5.12.5 Consent to Participate in the Research Biosample Repository

The Informed Consent Form will contain a separate section that addresses participation in the RBR. The investigator or authorized designee will explain to each patient the objectives, methods, and potential hazards of participation in the RBR. Patients will be told that they are free to refuse to participate and may withdraw their consent at any time and for any reason during the storage period. A separate, specific signature will be required to document a patient's agreement to provide optional RBR samples. Patients who decline to participate will not provide a separate signature.

The investigator should document whether or not the patient has given consent to participate and (if applicable) the date(s) of consent, by completing the RBR Research Sample Informed Consent eCRF.

In the event of an RBR participant's death or loss of competence, the participant's samples and data will continue to be used as part of the RBR research.

4.5.12.6 Withdrawal from the Research Biosample Repository

Patients who give consent to provide RBR samples have the right to withdraw their consent at any time for any reason. After withdrawal of consent, any remaining samples will be destroyed or will no longer be linked to the patient. However, if RBR samples have been tested prior to withdrawal of consent, results from those tests will remain as part of the overall research data. If a patient wishes to withdraw consent to the testing of his or her RBR samples during the study, the investigator must inform the Medical Monitor in writing of the patient's wishes through use of the appropriate RBR Subject Withdrawal Form and must enter the date of withdrawal on the RBR Research Sample Withdrawal of Informed Consent eCRF. If a patient wishes to withdraw consent to the testing of his or her RBR samples after closure of the site, the investigator must inform the Sponsor by emailing the study number and patient number to the following email address:

[contact]

A patient's withdrawal from this study does not, by itself, constitute withdrawal of consent for testing of RBR samples. Likewise, a patient's withdrawal of consent for testing of RBR samples does not constitute withdrawal from this study.

4.5.12.7 Monitoring and Oversight

RBR samples will be tracked in a manner consistent with Good Clinical Practice by a quality-controlled, auditable, and appropriately validated laboratory information management system, to ensure compliance with data confidentiality as well as adherence to authorized use of samples as specified in this protocol and in the Informed Consent Form. Sponsor monitors and auditors will have direct access to appropriate parts of records relating to patient participation in the RBR for the purposes of verifying the data provided to the Sponsor. The site will permit monitoring, audits, IRB/EC review, and health authority inspections by providing direct access to source data and documents related to the RBR samples.

4.6 TREATMENT, PATIENT, STUDY, AND SITE DISCONTINUATION

4.6.1 Study Treatment Discontinuation

Patients must permanently discontinue study treatment if they experience any of the following:

- Any medical condition that the investigator or Sponsor determines may jeopardize the patient's safety if he or she continues to receive study treatment
- Investigator or Sponsor determination that treatment discontinuation is in the best interest of the patient
- Intolerable toxicity related to study treatment determined by the investigator to be unacceptable in light of the potential for treatment benefit and the severity of the event
- Disease progression per investigator assessment according to RECIST 1.1, with the exception of isolated brain metastases (see Section 4.4.3)
- Symptomatic deterioration attributed to disease progression, as assessed by the investigator
- Non-compliance with protocol-specified drug administration and follow-up tests
- Concomitant use of any other (non-protocol) systemic anti-cancer therapy
- Pregnancy

The primary reason for study treatment discontinuation should be documented on the appropriate eCRF. Patients who discontinue study treatment will not be replaced.

Patients will return to the clinic for a treatment discontinuation visit 30 (+3) days after the final dose of study treatment (unless final dose resulted in a dose delay prior to decision to discontinue). For the control arm, the upper limit of the visit window will be dependent upon maximum dosing delay as permitted per local guidelines. The visit at which response assessment shows progressive disease may be used as the treatment discontinuation visit if it falls within 28 (+3) days after the patient's final dose of study treatment. After treatment discontinuation, adverse events will continue to be recorded as outlined in the schedule of activities (see [Appendix 1](#)).

Patients who discontinue study treatment for any reason other than unequivocal disease progression or death will continue to undergo tumor response assessments and PRO assessments as outlined in the schedule of activities (see [Appendix 1](#)).

After treatment discontinuation (regardless of the reason), information on survival follow-up and new anti-cancer therapy will be collected via telephone calls,

patient medical records, and/or clinic visits approximately every 6 months or more frequently until death (unless the patient withdraws consent or the Sponsor terminates the study).

Refer to the schedule of activities (see [Appendix 1](#)) for details on follow-up assessments to be performed for patients who discontinue study treatment. Patients who are unwilling to return to the clinic after treatment discontinuation will no longer undergo adverse event and tumor response assessments at clinic visits but can undergo follow-up for adverse events, survival, and new anti-cancer therapy via telephone calls.

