Patients will be followed for safety for 30 days after the final dose of study treatment, including a treatment discontinuation visit at 30 days after the final dose (unless final dose resulted in a dose delay prior to decision to discontinue). For the control arm, the upper limit of the visit window will be dependent upon maximum dosing delay as permitted per local guidelines. Thereafter, information on survival and new anti-cancer therapy will be collected every 6 months until death (unless the patient withdraws consent or the Sponsor terminates the study). The survival follow-up period for patients remaining in the study will conclude at the time of the final OS analysis.

After the date of randomization, tumor assessments will be performed every 8 weeks for the first 18 months, then every 12 weeks thereafter, with the

exception of bone scans, which will be performed every 24 weeks or as clinically indicated (see Section [4.5.6.2](#) for detailed information).

Efficacy analyses will be based on the local radiologist's or investigator's tumor assessments. Radiographic images, photographs, and clinical information will be sent to a blinded, independent core imaging laboratory to enable a retrospective evaluation of disease response and progression by an Independent Review Committee (IRC) (see Section [3.1.2](#)).

To evaluate the PK properties of GDC-9545, sparse PK samples will be collected at various timepoints before and after dosing from all patients in the GDC-9545 arm; a subset of patients in the GDC-9545 arm will be enrolled for intensive GDC-9545 PK sampling (see [Appendix 2](#)).

[figure not shown]
Patient-reported outcome (PRO) instruments will be completed by patients to evaluate the treatment impact from the patient's perspective.

Optional patient interviews will be performed among a subset (up to 30) of patients receiving GDC-9545, to explore patients' experience of study drug, therapeutic context, and disease journey.

All patients will be closely monitored for adverse events throughout the study, and adverse events will be graded according to NCI CTCAE v5.0. An IMC will also provide safety oversight as outlined in Section [3.1.3](#).

[Figure 1](#) presents an overview of the study design. A schedule of activities is provided in [Appendix 1](#).

Figure 1 Study Schema

ER=estrogen receptor; HER2=human epidermal growth factor receptor 2; LHRH=luteinizing hormone-releasing hormone; PO=orally; QD=once a day; R=randomization.

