5.3.1 Adverse Event Reporting Period

Investigators will seek information on adverse events at each patient contact. All adverse events, whether reported by the patient or noted by study personnel, will be recorded in the patient's medical record and on the Adverse Event eCRF.

After informed consent has been obtained but prior to initiation of study drug, only serious adverse events caused by a protocol-mandated intervention (e.g., invasive procedures such as biopsies, discontinuation of medications) should be reported (see Section 5.4.2 for instructions for reporting serious adverse events).

After initiation of study drug, all adverse events will be reported until 30 days after the final dose of study drug.

Instructions for reporting adverse events that occur after the adverse event reporting period are provided in Section 5.6.

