Appendix 1 Schedule of Activities

Day (Window)	Screening ^a		Treatment Cycles (28-day cycles)		Treatment Discontinuation Visit ^b	PRO Follow-Up	Follow-Up
			Cycles 1–2	Cycles 3 and Beyond			
	–28 to –1	–7 to –1	1 ^c (±3 days)	1 (±3 days)	30 Days after Final Dose (+3 days)	90 Days after TD (±7 days)	Every 6 months (±7 days) ^d
Informed consent	x ^e						
Demographic data	x						
Medical history and baseline conditions	x						
Vital signs ^f	x		x	x	x		
Weight	x		x	x	x		
Height	x						
Complete physical examination ^g	x						
Limited physical examination ^h			x	x	x		
12-lead ECG ⁱ	x		x	Day 1 of Cycle 4, then every four cycles thereafter	x		
LVEF ^j	x						
ECOG Performance Status	x		x	x	x		
Hematology ^k		x	x	x	x		
Chemistry ^l		x	x	x	x		

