- ^b Patients who discontinue study treatment will return to the clinic for a treatment discontinuation visit 30 (+3) days after their final dose of study treatment (unless final dose resulted in a dose delay prior to decision to discontinue). For the control arm, the upper limit of the visit window will be dependent upon maximum dosing delay as permitted per local guidelines. The visit at which response assessment shows progressive disease may be used as the treatment discontinuation visit if it falls within 28 (+3) days after the patient's final dose of study treatment.
- ^c Patients should receive their first dose of study treatment on the day of randomization, if possible, but no later than 3 business days after randomization.
- ^d Patients who experience disease progression will discontinue treatment (except in the case of isolated brain metastases as outlined in Section 4.4.3) and enter a follow-up period during which survival and new anti-cancer therapy information will be collected every 6 months or more frequently until death (unless the patient withdraws consent or the Sponsor terminates the study).
- ^e Informed consent must be documented before any study-specific screening procedure is performed and may be obtained up to 6 weeks before initiation of study treatment. Patients who do not meet the criteria for participation in this study (screen failure) must re-sign the consent form prior to re-screening.
- ^f Vital signs include respiratory rate, pulse rate, and systolic and diastolic blood pressure while the patient is in a seated position, and temperature.
- ^g Complete physical examination includes evaluation of the head eyes, ears, nose, and throat, and the cardiovascular, dermatologic, musculoskeletal, respiratory, gastrointestinal, genitourinary, and neurologic systems.
- ^h Perform a limited, symptom-directed examination at specified postbaseline timepoints and as clinically indicated at other timepoints.
- ⁱ 12-lead ECG recordings will be obtained during screening; on Day 1 of Cycles 1, 2, and 4; on Day 1 of every four cycles thereafter (i.e., Cycles 8, 12, 16, etc.); at the treatment discontinuation visit; and as clinically indicated at other timepoints. Patients should be resting in a supine position for at least 10 minutes prior to ECG recording (see Section 4.5.8).
- ^j LVEF to be measured using multiple-gated acquisition scan or echocardiogram.

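### The progression visit may replace the day-30 treatment discontinuation visit with no earliest day, so when it is used near the last dose no adverse-event contact is scheduled for the rest of the reporting period

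*Protocol*

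**What the plan says.** Protocol Section 3.1.1 states the commitment: "Patients will be followed for safety for 30 days after the final dose of study treatment, including a treatment discontinuation visit at 30 days". Section 4.6.1 gives the window: "Patients will return to the clinic for a treatment discontinuation visit 30 (+3) days after the final dose of study treatment". It makes exceptions for dose delays and for the upper limit in the control arm. Section 5.3.1 fixes the reporting period: "After initiation of study drug, all adverse events will be reported until 30 days after the final dose of study drug".

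Section 4.6.1 then allows a substitution: "The visit at which response assessment shows progressive disease may be used as the treatment discontinuation visit if it falls within 28 (+3) days" of the final dose. Appendix 1, footnote b, repeats that the visit "may be used as the treatment discontinuation visit if it falls within 28 (+3) days after the patient's final dose of study treatment". Neither place names a first permissible day.

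On how AEs are found, Section 5.3.1 says: "Investigators will seek information on adverse events at each patient contact". For recording after discontinuation, Section 4.6.1 refers to Appendix 1, where the AE row is last marked in the treatment discontinuation column. The next column is PRO follow-up, "90 Days after TD", and then survival follow-up every 6 months. Neither is marked for AEs. For patients unwilling to return to the clinic, Section 4.6.1 says they "can undergo follow-up for adverse events, survival, and new anti-cancer therapy via telephone calls".

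**The concern.** The substitution rule has an upper limit but no lower one. Read literally, a progression visit on the day of the last dose qualifies as the visit planned for day 30. The AE query, laboratory tests, ECG and pregnancy test of that visit are then done before any post-treatment time has passed, and nothing else is scheduled until after the reporting period has closed.

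At stake is how new events are found in the 30 days after the last dose. They include events reportable within 24 hours under Section 5.2.3, such as Grade 3 or higher transaminase elevation and Grade 2 or higher bradycardia or thromboembolism. Without a scheduled contact, they reach the database only if the patient calls or is seen for another reason. The time from last dose to the progression visit may also depend on the drug, so completeness of capture could differ between treatments.

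**Working it through.** The plan gives no figure for this point. The check compares visit windows, counted in days after the final dose.

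**1. Windows**
- Planned visit, 30 (+3): day 30 to 33.
- Substitute visit, within 28 (+3): day 0 to 31 on the literal reading.
- If 28 (+3) is instead read as a window, it is day 28 to 31. Days 28 and 29 still precede the planned visit, so the two intervals disagree on either reading.

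**2. Days of the reporting period left without a scheduled AE contact**

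Formula: max(0, 30 − x), where x is the day of the substitute visit.

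| x | Days left | Share of 30 |
|---|---|---|
| 0 | 30 | 100% |
| 1 | 29 | 97% |
| 7 | 23 | 77% |
| 14 | 16 | 53% |
| 28 | 2 | 7% |

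**3. Next scheduled contact**

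After a day-0 substitution: 0 + 90 ± 7 = day 83 to 97. Footnote v allows this follow-up by a web-based system. Section 5.3.5.13 says sites are not expected to review PRO data for AEs.

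**4. Where x is likely to fall (inference from the schedules)**
- Scans every 8 weeks = 56 days = 2 × 28, so scheduled scans fall near Day 1 of Cycles 3, 5, 7 and so on. The match is loose: scans have a ±7-day window, run from randomization and ignore dose delays (Section 4.5.6.2).
- GDC-9545 is taken daily and treatment continues to progression. A patient found to have progressed at such a visit would be at about x = 0 or 1. A daily oral aromatase inhibitor would behave in the same way.
- Sections 1.2.1 and 3.3.1 describe fulvestrant as monthly. If the injection due at that visit is not given, x is about 28 and 2 days are uncovered. This assumes the previous injection was on time; control dosing follows local prescribing information (Section 4.3.2.2).

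**5. Ceiling on the number who could be eligible**

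Inputs: design medians 5.5 and 8.5 months, 10% annual loss to follow-up, and the accrual in SAP Table 2 (sums to 300). With h = ln 2 / median and d = −ln(0.9)/12, expected events at month T are the sum over both arms and accrual months j of (r_j/2) × h/(h+d) × [1 − exp(−(h+d)(T − j + 0.5))].
- Month 18: 170 (57%). The plan's own figure is about 166 events at about 18 months, 166/300 = 55%, so the projection is close.
- Month 24: 73%. Month 30: 82%. Month 40: 88%.

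These counts include deaths without progression and say nothing about use of the option. They bound eligibility under the design assumptions and do not measure lost contacts. Section 1.2.2.2 reports AE withdrawals of 2 + 3 = 5 of 303 (1.7%), so progression is probably the main reason for stopping, but no count by reason is given.

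**The case against.** The case on the other side is substantial, and most of it stands against stronger readings of the text.

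- **Most patients lose their safety contact.** A reader might infer this from 166/300. The documents do not support it. The option is permissive and its use is not reported. The 166 pools both arms and counts deaths. At the design hazard ratio fewer than half of those events, so fewer than 83 of 300 (28%), would be in the GDC-9545 arm, and the aromatase inhibitor share of the control arm is not given. A progression visit later in the window is itself a contact within the 30 days.
- **AE observation time is cut.** Taking 5.5 months as 167 days, one could compute 30/(167 + 30) = 15%. The reporting period is not shortened: Sections 5.3.1 and 5.4.2.2 and Appendix 1, footnote y, all keep it at 30 days. The sum also treats median PFS as treatment duration. What may be lost is a scheduled contact.
- **Known findings go unresolved.** Section 5.5.1 requires each AE to be followed until it resolves to baseline grade or better or is assessed as stable, with no day-30 limit. The gap concerns new events.
- **Pregnancies are missed.** Section 5.4.3 instructs patients to report a pregnancy within 10 days after the final GDC-9545 dose and requires sponsor notification within 24 hours. That route works without a visit.
- **The comparison between arms is biased.** The fulvestrant share and actual visit timings are unknown, so a difference is possible but not shown.

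These points do not remove the core. A duty to report is not a scheduled occasion to ask. Section 4.6.1 sends recording to a schedule that has no such occasion after the substituted visit. Telephone follow-up is optional and stated only for patients unwilling to return.

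**Conclusion.** The point holds in a limited form. Sections 3.1.1 and 4.6.1 and Appendix 1, footnote b, do not agree on when the discontinuation visit may take place. Because the substitution has no earliest day, patients for whom it is used at or near the last dose have no scheduled AE contact for the rest of the 30-day period.

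Per affected patient, the uncovered stretch runs from 30 days (day-0 visit) to 2 days (day-28 visit). If 28 (+3) was meant as a day 28 to 31 window, the uncovered stretch is at most 2 days and the point reduces to mismatched intervals. A longer gap is most likely with daily oral drugs. The possible difference from monthly fulvestrant rests on the dosing schedules and on an on-time injection not being given at the progression visit. The number of patients affected cannot be derived from the documents.

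The SAP does not address this. Section 5.6.2 defines treatment-emergent events only by onset after the first dose and summarizes them by arm, with no account of contact after the last dose.

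**What to change.** 1. Reconcile Protocol Sections 3.1.1 and 4.6.1 and Appendix 1, footnote b. State which interval is intended where 28 (+3) and 30 (+3) now differ, and whether the substitution has an earliest day.
2. Keep the progression-visit option, and add to Section 4.6.1 and as an entry in Appendix 1: when the progression visit serves as the treatment discontinuation visit before day 30, the site contacts the patient at 30 (+3) days after the final dose, by telephone if preferred, to collect AEs, serious AEs, AEs of special interest and pregnancy status.

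No added rule on laboratory or ECG follow-up is needed, because Section 5.5.1 already governs identified AEs.

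The cost is protocol wording and one call per affected patient. Telephone contact is already accepted in Section 4.6.1, though only as an option for patients who decline visits. The benefit is limited: the Version 4 amendment rationale says enrollment is complete. Section 1.2.2.2 reports that at the 18 February 2022 cutoff 15.2% had left the study and most of the remainder had stopped treatment. The call can help only patients still on treatment.
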